BOTOX

## 3.0 LIST OF ABBREVIATIONS

AE adverse event

ANCOVA analysis of covariance BMI body mass index

BOTOX Botulinum toxin type A purified neurotoxin

bpm beats per minute

CMH Cochran-Mantel-Haenszel eCRF electronic case report form FWER familywise error rate

MCMC Markov chain Monte Carlo

MI multiple imputation

MCP multiple comparisons procedure

mITT modified Intent-to-Treat

MMP masseter muscle prominence

MMPS Masseter Muscle Prominence Scale

MMPS-P Masseter Muscle Prominence Scale – Participant

OL Open-Label

PCS potentially clinically significant

PDSOT possible distant spread of toxin

PSAC Participant Self-Assessment of Change

Q1 first quartile Q3 third quartile

SAE serious adverse event
SAP statistical analysis plan
SD standard deviation
SoA Schedule of Activities

TEAE treatment-emergent adverse event

TESAE treatment-emergent serious adverse event

U unit

WHO World Health Organization

## 4.0 INTRODUCTION

This statistical analysis plan (SAP) provides a more technical and detailed elaboration of the statistical analyses of the efficacy and safety data as outlined and/or specified in the final protocol of Study 1789-301-008 (version dated 17 Dec 2018). Specifications of tables, figures, and data listings are contained in a separate document.

This is an 18-month, multicenter study consisting of 2 periods, a double-blind placebo-controlled single-treatment period and an open-label period in which a maximum of 2 further study treatments can be received. Up to 20 scheduled visits are planned: screening (Day -14 to Day -1), baseline (Day 1), follow-up monthly thereafter (Days 30, 60, 90, 120, 150, 180, 210, 240, 270, 300, 330, 360, 390, 420, 450, 480, 510), and study exit (Day 540).

Period 1 (Days 1 through 180) will be a double-blind, randomized, placebo-controlled, single-treatment design, which will assess the safety and efficacy of botulinum toxin type A purified neurotoxin (BOTOX) treatment of masseter muscle prominence (MMP). On Day 1, participants will be randomized in a 3:1 ratio to receive BOTOX 72 unit (U) or placebo. Randomization will be stratified at each investigator site by the participant's baseline Masseter Muscle Prominence Scale (MMPS) Grade (4 or 5). On Day 180, final Period 1 assessments will be collected, after which all participants will continue into Period 2, the open-label treatment portion of the study.

Period 2 (Days 180 through 540) will be open-label. All BOTOX and placebo-treated participants from Period 1 are eligible to receive up to 2 open-label treatments of BOTOX 72 U in Period 2 if they meet protocol-specified retreatment criteria on or after the Day 180 visit. If the participant does not meet the retreatment criteria at the Day 180 visit, he or she will be reassessed at the next visit. For Treatment 2, participants who qualify can be retreated from the Day 180 visit through the Day 420 visit.

#### Retreatment Criteria:

- Participant has presence of MMP of at least marked (Grade 4) on each side, as assessed by the investigator using the MMPS, AND
- Females of childbearing potential must have a negative pregnancy test prior to treatment,
   AND

•

If a participant qualifies for retreatment in Period 2 and declines it, retreatment will not be administered at that visit and the participant's reason for declining retreatment will be captured on the electronic case report form (eCRF). If the participant still meets retreatment criteria at the next visit he or she may receive retreatment at that time.

Table 1. Schedule of Activities (SoA)

	Period 1: Double-blind treatment (BOTOX or placebo)			Period 2: Open-label treatment (BOTOX)				
	Visit 1	Visit 2	Visits 3-7	Visit 8	3	Visits 9-16	Visits 17-19	Visit 20
Study Procedures	Screening	Baseline a Day 1	Follow-Up Days 30, 60, 90, 120, 150	Follow-1 Retreatm	ent b	Follow-Up/ Retreatment b Days 210, 240, 270, 300, 330, 360, 390, 420	Follow-Up  Days 450, 480, 510	Study Exit c Day 540
Visit Windows	Day -14 to Day -1	-	± 7 Days	± 7 days		± 7 Days	± 7 Days	± 7 Days
Informed Consent, Privacy Authorization	X							
Training for MMPS-P and PSAC d	X							
Inclusion/Exclusion Criteria	Xe	X						
Demographics	X							
Medical/Surgical History	X							
Concomitant Medications/Procedures	X	X	X	X		X	X	X
Height	$\mathbf{X}^{\mathbf{f}}$							
Body Weight	$\mathbf{X}^{\mathbf{f}}$	X	X	X		X	X	X
Vital Signs (blood pressure, respiratory rate, pulse rate)		x	х	x		x	х	x
Pregnancy Test g	x	х		X (if retreatmy visit)	nent	X (if retreatment visit)		x
Standardized Imaging	Xh	X	X	Х		X	X	X

	Period 1: Double-blind treatment (BOTOX or placebo)		ıt	Period 2: Open-label treatment (BOTOX)			ent	
	Visit 1	Visit 2	Visits 3-7	Visit 8		Visits 9-16	Visits 17-19	19 Visit 20
Study Procedures	Screening	Baseline a Day 1	Follow-Up Days 30, 60, 90, 120, 150	Follow Retreat	ment b	Follow-Up/ Retreatment b Days 210, 240, 270, 300, 330, 360, 390, 420	Follow-Up  Days 450, 480, 510	Study Exit c Day 540
Clinical Outcome Assessments:								
Masseter Muscle Prominence Scale – Participant (MMPS-P) i	x	x	x	x		x	x	x
Masseter Prominence Participant Self- Assessment of Change j (PSAC)			x	x		x	x	X
Participant Lower Facial Shape Questionnaire (LFSQ)- Sign Assessment	X	x	х	x		x	x	х
Participant Global Impression of Bother (PGIB) i	X	x	x	x		x	x	X
LFSQ- Impact Assessment	X	X	X	X		X	X	X
LFSQ- Satisfaction Assessment	X	X	X	X		X	X	X
LFSQ- Treatment Satisfaction Assessment (Baseline Version)	х	X						
LFSQ- Treatment Satisfaction Assessment (Follow-up Version)			х	x		x	x	х
Masseter Muscle Prominence Scale (MMPS) – Investigator Assessment	Xk	X k	х	х		x	х	х
Randomization		X						
Study Intervention 		x		X b (if retreativisit)	tment	X b (if retreatment visit)		
Adverse Events m	X	X	X	X		X	X	X

[figure not shown]
- a. All baseline (Day 1) study procedures, from confirmation of all study inclusion/exclusion criteria through imaging, must be completed before randomization and study treatment (BOTOX or placebo). Randomization will be stratified at each investigator site by the participant's baseline MMPS Grade (4 or 5).
- b. Participants must meet retreatment criteria to receive up to 2 open-label study treatments with BOTOX. For Treatment 2, participants who qualify can be retreated from the Day 180 visit through the Day 420 visit. For Treatment 3, the earliest visit that participants may qualify and receive the third treatment is the Day 270 visit (3 months after the earliest visit for Treatment 2).
- Or early discontinuation from the study. All exit assessments should be completed as soon as possible after a decision to discontinue a participant from the study.
- Training on the MMPS-P and PSAC may be repeated at other visits, as needed.
- e. During the evaluation of inclusion criteria at the Screening Visit, MMPS, standardized imaging, and MMPS-P evaluations will be completed (in that order) prior to other COAs. All other procedures at Screening are suggested to be performed in the order listed in the table.
- f. At the Screening Visit, height and weight will be used to calculate BMI to determine eligibility for enrollment. BMI = weight (kg)/[height (m)].
- g. Females of childbearing potential must have a negative test result before receiving study treatment/retreatment. This test may also be performed at any other visit, at the investigator's discretion. At each visit, the investigator should discuss contraceptive use compliance with females of childbearing potential. Urine tests will be used unless the study site requires the use of serum testing, in which case serum tests will be used.
- h. Prior to Day 1, Canfield Scientific, Inc. must review and accept each participant's screening images; 1 retake will be allowed before Day 1 if the screening images are not acceptable.
- The MMPS-P and PGIB will be conducted using the images collected at the current visit. If retakes are required for the screening images, the MMPS-P and PGIB will be collected again at the image retake visit, using the new images.
- j. The PSAC will be conducted using images from the current visit and the Baseline Visit (unless the Baseline images did not pass validation by Canfield, in which case the Screening images will be used instead).
- Investigator MMPS should be conducted prior to other COAs at the Screening and Baseline visits (only). At all other visits, it should occur after the other COAs.
- Prepared by an IDR in Period 1 and injected by the investigator in both Periods 1 and 2. After completing injections on one side of the lower face, direct pressure should be applied to the injection sites for approximately 30 seconds before injecting the other side. Participant should be observed at least 30 minutes after the injections for AEs.
- M. At each treatment visit, AEs must be collected both before and after study treatment.

# 5.0 STUDY OBJECTIVES AND CLINICAL HYPOTHESES

## 5.1 STUDY OBJECTIVES

The primary and secondary objectives of this study are to compare the efficacy and safety of BOTOX versus placebo in participants with MMP.

Objectives	Endpoints					
Primary						
To compare the efficacy of BOTOX with placebo in participants with bilateral MMP	
 
Achievement of ≥ 2-grade improvement from baseline at Day 90, per investigator assessments of MMP using the MMPS (5 severity grades: 1 = minimal, 2 = mild, 3 = moderate, 4 = marked, 5 = very marked)
 
					
To compare the safety of BOTOX with placebo in participants with MMP	Incidence of adverse events (AEs) and change from baseline in vital signs					
Secondary						
To compare the efficacy of BOTOX with placebo in participants with MMP	
 
Achievement of MMPS Grade ≤ 3 at Day 90, according to investigator
 
Achievement of MMPS-P Grade ≤ 3 at Day 90, according to participant
 
Achievement of ≥ 2-grade improvement from baseline at Day 90 using the Masseter Muscle Prominence Scale - participant (MMPS-P)
 
Achievement of Participant Self-assessment of Change (PSAC) Grade ≥ 1 (at least minimally improved from baseline) at Day 90
 
Change from baseline in lower facial width (mm) at Day 90, calculated from standardized images
 
Duration of effect for BOTOX-treated MMPS responders
 
					

## 5.2 CLINICAL HYPOTHESES

BOTOX treatment of MMP is more effective than placebo as measured by investigator assessment of MMP severity using the MMPS.

BOTOX has an acceptable safety profile after single and repeat MMP treatment.

## 6.0 PARTICIPANT POPULATIONS

## 6.1 MODIFIED INTENT-TO-TREAT POPULATION

The Modified Intent-to-Treat (mITT) Population will consist of all randomized participants with at least one postbaseline MMPS assessment. For efficacy analyses, data will be analyzed according to participants' randomization assignments, regardless of actual treatment received.

## 6.2 SAFETY POPULATION

The Safety Population will consist of all participants who received at least one dose of study treatment. All safety analyses will be performed using the Safety Population. For safety analyses, the participants will be analyzed according to actual treatment received (rather than as randomized).

## 7.0 PARTICIPANT DISPOSITION

The number and percentage of participants in the study populations (Safety, and mITT) will be summarized by treatment group which will include both the cycle 1 and Open-Label (OL) treatments (e.g., cycle 1 treatment/OL treatment). The number of participants screened will be summarized overall only.

The number and percentage of participants who receive injection, complete, and prematurely discontinue within each treatment cycle will be presented for each treatment group and pooled across treatment groups for all randomized participants. The reasons for premature discontinuation from each treatment cycle as recorded on the termination pages of the eCRF will be summarized (number and percentage) by treatment group for all randomized participants. All participants who prematurely discontinue during each treatment cycle will be listed by discontinuation reason for all randomized participants.

## 8.0 DEMOGRAPHICS AND OTHER BASELINE CHARACTERISTICS

#### 8.1 DEMOGRAPHICS AND BASELINE CHARACTERISTICS

Demographic parameters (age; age group; race; race group [Asian with Asian subgroups, non-Asian]; ethnicity; sex; country/region [Canada, China, Taiwan]), baseline characteristics (weight; height; and body mass index, calculated as weight [kg]/(height [m]), baseline MMPS Grade, and baseline MMPS-P Grade) will be summarized descriptively by treatment group for the mITT Population. Continuous variables will be summarized by number of participants and mean, standard deviation (SD), median, first quartile (Q1), third quartile (Q3), minimum, and maximum values. Categorical variables will be summarized by number and percentage of participants.

#### 8.2 MEDICAL HISTORY

Medical history, encompassing abnormalities and surgeries reported as occurring before Day 1, will be coded using the Medical Dictionary for Regulatory Activities (MedDRA), version 25.1 or newer. Unique participants who report medical history events will be summarized by MedDRA system organ class (SOC) and preferred term (PT) for the mITT Population by treatment group.

#### 8.3 PRIOR AND CONCOMITANT MEDICATIONS

Medications will be coded using the World Health Organization (WHO) Drug Dictionary. Prior medications are medications taken  $\geq 1$  time before the study intervention start date, regardless of medication end date. Concomitant medications are medications taken  $\geq 1$  time on or after the study intervention start date, regardless of medication start date. Unique participants who reported medications will be summarized by WHO Drug class and preferred drug name for the mITT Population by treatment group. Prior and concomitant medications will be summarized separately.

## 9.0 EFFICACY ANALYSES

The efficacy analyses will be based on the mITT population. Baseline for efficacy is defined as the last approved (imaging data) non-missing efficacy assessment before the first dose of study treatment. Pairwise comparisons will be conducted between BOTOX 72 U group and the placebo group. All statistical tests will be 2-sided hypothesis tests performed at 5% level of significance for main effects, with Type I error controlled as described further in Section 14.0.

For the primary and secondary efficacy variables, subjects with missing values at a given visit will be imputed using multiple imputation (MI) up to Day 180 in Period 1. The other efficacy variables will not be imputed.

For subjects who continue in Period 2, efficacy visits beyond Day 180 but prior to retreatment (if any) will be displayed by assigned treatment group in double-blind treatment cycle 1.

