Danied 2 (Davis 190 through 540/Study Evit)

Period 2 (Days 180 through 540/Study Exit)

Day 180 is considered both the end of Period 1 and the beginning of Period 2. After Period 1 assessments are collected, the participant will enter Period 2 and will be assessed for retreatment. If the participant does not meet the retreatment criteria at Day 180, he or she will be reassessed at the next visit. All BOTOX and placebo-treated participants from Period 1 are eligible to receive up to 2 open-label treatments of BOTOX 72 U in Period 2 *if* they meet the following retreatment criteria (also see Section 6.6) on or after the Day 180 visit.

- Participant has bilateral marked (Grade 4) or very marked (Grade 5) MMP, as assessed by the investigator using the MMPS, AND
- Females of childbearing potential must have a negative pregnancy test prior to treatment,
 AND
- If it is the third treatment, at least 3 months have lapsed since the previous study treatment (no retreatment earlier than 84 days)

During Period 2, participants will attend all follow-up visits (Days 210, 240, 270, 300, 330, 360, 390, 420, 450, 480, 510, and 540). For Treatment 2, participants who qualify can be retreated from the Day 180 visit through the Day 420 visit. For Treatment 3, the earliest visit that participants may qualify and receive the third treatment is Day 270 (3 months after the earliest visit for Treatment 2 [Day 180]). The last day that a participant can receive either Treatment 2 or 3 is Day 420; this ensures a 120-day safety and efficacy follow-up period by Day 540/study exit. A participant who meets retreatment criteria may decline retreatment if they choose, and their reason will be captured on the eCRF. If the participant still meets retreatment criteria at the next visit (up to Day 420), he or she may receive retreatment at that time.

In Period 2, participants will receive up to 2 additional treatments. Based on individual variability in time to meet retreatment criteria noted in the Phase 2 Study 191622-130, retreatment timepoints are not expected to be synchronized among the participants in the study.

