#### 9.1 PRIMARY EFFICACY ENDPOINT

The primary efficacy assessment is masseter muscle prominence assessed by the investigator using the MMPS (1 = minimal, 2 = mild, 3 = moderate, 4 = marked, 5 = very marked).

The primary efficacy endpoint is the achievement of  $\geq$  2-grade improvement from baseline at Day 90 using the MMPS.

The following set of hypotheses will be used to compare the BOTOX 72 U group with placebo:

- Null hypothesis: BOTOX and placebo are equally effective in reducing MMP as measured by the proportion of participants achieving ≥ 2-grade improvement from baseline at Day 90 using the MMPS.
- Alternative hypothesis: BOTOX and placebo are not equally effective in reducing MMP as measured by the proportion of participants achieving ≥ 2-grade improvement from baseline at Day 90 using the MMPS.

The proportion of participants who achieve  $\geq$  2-grade improvement from baseline, per investigator assessments of MMP using the MMPS, will be analyzed using Cochran-Mantel-Haenszel (CMH) model stratified by baseline MMPS Grade (4 or 5) at each visit. A 2-sided p-value  $\leq$  0.05 will be claimed as statistically significant. The Breslow-Day homogeneity of the odds-ratio test will be performed to test the interaction of treatment by baseline MMPS Grade. A

two-sided p-value  $\leq$  0.1 will be claimed as statistically significant. Responder rate 2-sided 95% CIs within each treatment group will be based on normal approximation to the binomial.

Sensitivity analyses will be performed for the primary efficacy variable based on observed data.

The attributes of the estimands corresponding to the primary efficacy endpoint are summarized in Table 2.

Table 2. Summary of the Estimand Attributes of the Primary Efficacy Endpoint

	Attributes of the Estimand							
Estimand Label	Treatment	Endpoint	Population	Handling of Intercurrent Events	Statistical Summary			
Hypothetical estimand for primary endpoint	BOTOX 72 U vs placebo	Achievement of ≥ 2-grade improvement from baseline based on MMPS at Day 90	mITT (all randomized participants with at least one postbaseline MMPS assessment)	Participants who discontinue prior to Day 90 assessments or who do not have Day 90 MMPS assessments will be included in the analysis as a hypothetical scenario in which they had not missed the MMPS assessments	Difference in response proportions between treatments after MI using CMH test stratified by baseline MMPS			

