## 9.2 SECONDARY EFFICACY ENDPOINTS

The secondary efficacy endpoints are:

- Achievement of MMPS Grade ≤ 3 at Day 90, according to investigator
- Achievement of MMPS-P Grade ≤ 3 at Day 90, according to participant
- Achievement of ≥ 2-grade improvement from baseline at Day 90 using the MMPS-P
- Achievement of PSAC Grade ≥ 1 (at least minimally improved from baseline) at Day 90
- Change from baseline in lower facial width (mm) at Day 90

Duration of effect for BOTOX-treated MMPS responders

The proportion of participants who achieve MMPS Grade  $\leq$  3, the proportion of participants who achieve MMPS-P Grade  $\leq$  3, the proportion of participants who achieve  $\geq$  2-grade improvement from baseline using the MMPS-P, and the proportion of participants who achieve PSAC Grade  $\geq$  1 will be analyzed in the same manner as that used to analyze the primary endpoint. Missing MMPS, MMPS-P, and PSAC values in Period 1 will be imputed using the same MI method as for primary endpoint.

Table 3. Summary of the Estimand Attributes of the Secondary Efficacy Endpoints

	Attributes of the Estimand								
Estimand Label	Treat- ment	Endpoint	Population	Handling of Intercurrent Events	Statistical Summary				
Hypothetical estimand for binary secondary endpoints	BOTOX 72 U vs placebo	Achievement of the following at Day 90:  • MMPS Grade ≤ 3  • MMPS-P Grade ≤ 3  • MMPS-P ≥ 2-grade improvement from baseline  • PSAC Grade ≥ 1	mITT (all randomized participants with at least one postbaseline MMPS assessment)	Participants who discontinue prior to Day 90 assessments or who do not have specified Day 90 secondary efficacy assessments will be included in the analysis as a hypothetical scenario in which they had not missed the assessments	Difference in response proportions between treatments after MI using CMH test stratified by baseline MMPS				
Hypothetical estimand for continuous secondary endpoints	BOTOX 72 U vs placebo	Change from baseline in lower facial width (mm) at Day 90	mITT (all randomized participants with at least one postbaseline MMPS assessment)	Participants who discontinue prior to Day 90 assessments or who do not have Day 90 lower facial width will be included in the analysis as a hypothetical scenario in which they had not missed the lower facial width assessments	Difference between treatments in LS Mean and SE after MI using ANCOVA				

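### After Day 180 the SAP displays efficacy by randomised arm only until retreatment; if retreated participants leave the denominator, the late MMPS responder rates are selected on the outcome and overstate response

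*SAP*

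**What the plan says.** SAP 9.0 bases efficacy analyses on the mITT population and states that "efficacy visits beyond Day 180 but prior to retreatment (if any) will be displayed by assigned treatment group in double-blind treatment cycle 1". In the same section, missing primary and secondary values "will be imputed using multiple imputation (MI) up to Day 180 in Period 1"; the readable text gives no handling rule for later visits.

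The severity criterion for retreatment in SAP 4.0 is "Participant has presence of MMP of at least marked (Grade 4) on each side, as assessed by the investigator using the MMPS". Protocol 4.1 has the same threshold: "Participant has bilateral marked (Grade 4) or very marked (Grade 5) MMP, as assessed by the investigator using the MMPS". Protocol 6.6.1 allows retreatment at every visit from Day 180 to Day 420, and protocol 4.1 does not expect participants to be retreated at the same time. Retreatment may be refused: "If a participant qualifies for retreatment in Period 2 and declines it, retreatment will not be administered at that visit".

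The primary responder definition is an improvement of at least 2 MMPS grades at Day 90. The first secondary is "Achievement of MMPS Grade ≤ 3 at Day 90, according to investigator". The responder analysis in SAP 9.1 is a CMH analysis "stratified by baseline MMPS Grade (4 or 5) at each visit", and SAP 9.2 treats the binary secondary endpoints in the same way. Neither section says that this stops at Day 180. SAP 9.2 also lists duration of effect, for BOTOX-treated MMPS responders only.

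**The concern.** Leaving the by-arm display is triggered by the variable being displayed. Inclusion criterion 2.02 requires baseline Grade 4 or 5. A participant at Grade 4 or 5 therefore fails Grade 3 or lower, and also fails the 2-grade definition: from baseline 4 that needs Grade 2 or lower, and from baseline 5 it needs Grade 3 or lower. Each visit from Day 180 can thus take current MMPS non-responders out of the set shown at the next visit, and the removal accumulates.

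At stake is how a reader sees persistence beyond six months. A percentage under a randomised-arm label is normally taken as that arm's response rate. Here it could be the rate among those who had not yet lost response or had refused retreatment. Placebo is likely to lose a larger share of its participants, so the two arms would be selected to different degrees. If the by-visit CMH analysis ran on these sets, it would compare groups that randomisation no longer protects.

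**Working it through.** **Figures from the documents.** The only stated figures that bear on this are the arm sizes, and they reproduce: 360 × 0.85 = 306 completers, and the 3:1 split gives 360 × 3/4 = 270 BOTOX and 360 × 1/4 = 90 placebo. No late response, loss or uptake rate is readable. Every rate below is an assumption.

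**Direction.** With R responders among N, removing k current non-responders changes R/N to R/(N − k). This is larger whenever R > 0 and k > 0.

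**One step, Day 180 to Day 210, Grade 3 or lower.** Let S be the share responding at Day 180, u the share of Grade 4–5 participants retreated, and 85% the share of Day 180 responders still responding at Day 210.

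- Rate over the whole arm, retreated counted as non-responders: 0.85 × S
- Rate among those not yet retreated: 0.85 × S / (1 − u(1 − S))

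Example, BOTOX, S = 60%, u = 75%: 0.51 / (1 − 0.75 × 0.40) = 0.51 / 0.70 = 72.9%, against 51.0%.

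| Arm, S | Whole arm | u = 25% | 50% | 75% | 100% |
|---|---|---|---|---|---|
| BOTOX, 60% | 51.0% | 56.7% | 63.8% | 72.9% | 85.0% |
| BOTOX, 40% | 34.0% | 40.0% | 48.6% | 61.8% | 85.0% |
| Placebo, 20% | 17.0% | 21.3% | 28.3% | 42.5% | 85.0% |
| Placebo, 10% | 8.5% | 11.0% | 15.5% | 26.2% | 85.0% |
| Placebo, 5% | 4.3% | 5.6% | 8.1% | 14.8% | 85.0% |

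The gap is 5.7 to 51.0 points for BOTOX. For placebo it is 2.5 to 76.5 points at S = 10%, and 1.3 (S = 5%, u = 25%) to 80.8 (S = 5%, u = 100%) over all three rows. At S = 10% the placebo n shown falls from 90 to about 70, 50, 29 and 9.

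**Shape of the curve.** The displayed Day 210 rate equals the Day 180 rate when 1 − u(1 − S) = 0.85, that is u = 0.15/(1 − S). For S = 60% this is 37.5%. Below that uptake the displayed rate falls, but less than the whole-arm rate; above it, the displayed rate rises.

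**Arm difference.** Take S = 60% and 10%. The whole-arm difference at Day 210 is 51.0 − 8.5 = 42.5 points. Displayed, it is 45.7, 48.3, 46.7 and 0 points at u = 25%, 50%, 75% and 100%. Now repeat the step to Day 360 at u = 75%. BOTOX is 0.60 × 0.85⁶ = 22.6% over the whole arm and 80.0% displayed (n about 76). Placebo is 0.10 × 0.85⁶ = 3.8% and 79.6% (n about 4). The difference is 18.8 points over the whole arms and 0.4 displayed.

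**Other assumptions.** Take S = 60% and 15%, monthly loss 10% (BOTOX) and 5% (placebo), and 90% uptake. Day 270 shows 89% against 44% for BOTOX and 94% (about 12 left) against 13% for placebo. At 60% uptake it shows 81% against 44%, and 66% against 13%.

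**The 2-grade definition.** If 25% of an arm respond at Day 210 and S = 50%, the displayed rate is 0.25/0.75 = 33.3% at u = 50% and 0.25/0.50 = 50.0% at u = 100%. An arm with no responders stays at 0%.

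**The retreatment-day assessment.** SAP 17.2 ends a cycle on the day before the next treatment. Read literally, a qualifying Grade 4–5 assessment made on the retreatment day also falls outside cycle 1. In the 72.9% example the rate becomes 0.51 / (0.51 + 0.25 × (0.40 × 0.25 + 0.60 × 0.15)) = 0.51/0.5575 = 91.5%.

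**The case against.** The strongest reply is that the sentence in SAP 9.0 is an attribution rule, not a denominator rule. The parallel sentence in SAP 10.0 ascribes safety data from the same window to the cycle 1 treatment, and SAP 9.0 opens by naming the mITT population. Table specifications are in a separate document, and SAP 9.3 and 12.0 are only headings in the public text. A denominator, an n per visit or a label may already exist there. This stands, and it is why the point is conditional.

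It is also fair that a rate among participants not yet retreated is a correct conditional summary, and that counting retreatment as non-response answers a different question. To call the displayed percentages wrong would go too far; the problem is that they would be read as the arm's rate. The comparison also assumes that those removed would mostly have stayed non-responders without retreatment.

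Selection is incomplete. Participants who decline stay in, as do those not at Grade 4 or worse on both sides. For the 2-grade definition, a participant who went from Grade 4 to Grade 3 is a non-responder who cannot qualify. This weakens the effect without reversing it. For MMPS-P, PSAC and facial width the selection acts only through their correlation with MMPS.

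That the display is merely descriptive is not a full answer, because the by-visit CMH analysis has no readable end at Day 180. The duration endpoint means the late displays are not the only evidence on persistence, but it has no placebo arm and starts from responders, so it does not supply an all-randomised rate.

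**Conclusion.** The point holds conditionally. If the late denominator is participants not yet retreated, which is the natural reading of an observed-data display, MMPS responder rates after Day 180 overstate the arm's response whenever it has responders and some non-responders are retreated. The direction follows from the retreatment threshold and the responder definitions. The size rests wholly on assumed response, loss and uptake rates, hence the wide ranges.

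A reader might infer that BOTOX response must appear to rise while it truly falls, or that the arm difference must vanish or reverse. The documents support neither. At 25% uptake with 60% responding at Day 180, the displayed BOTOX rate falls to 56.7%. The displayed difference can be wider or narrower than the whole-arm one, and it reverses only under some assumptions, such as slower loss in placebo with high uptake.

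Nor is the confirmatory result touched. The primary and comparative secondary endpoints are at Day 90, so familywise error control is unaffected. Day 180 data are also safe, because under protocol 4.1 "After Period 1 assessments are collected, the participant will enter Period 2 and will be assessed for retreatment".

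**What to change.** Add to SAP 9.0, for visits after Day 180:

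- For MMPS Grade 3 or lower and MMPS improvement of at least 2 grades, use all mITT participants of the randomised arm as denominator. Count a participant as a non-responder from the retreatment visit on. The qualifying grade already fails both definitions, so no modelling is needed.
- State separately how dropouts and missed visits without retreatment are handled. Dropout of 15% is anticipated and imputation ends at Day 180; these participants should not silently become failures.
- Show, per arm and visit, the number retreated and the number not yet retreated.
- For MMPS-P, PSAC and lower facial width, end the by-arm display at Day 180, or label it as participants not yet retreated, with n per visit and no arm comparison.
- State that the by-visit CMH comparison is not run on the not-yet-retreated subset after Day 180.
- Reconcile SAP 17.2 with SAP 9.0 on whether an assessment made on the retreatment day, before injection, belongs to cycle 1.

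If the table specifications already contain such rules, a cross-reference in SAP 9.0 is enough. Nothing changes in study conduct or in the retreatment criteria. The cost is a few lines of SAP text, slightly more table work, and less favourable late-visit percentages.
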